Project Title: Safety and Efficacy of High-Intensity Macrofocused

Ultrasound for Solar Lentigo in Chinese Population: A Prospective Study

Sponsor: The First Affiliated Hospital of Nanjing Medical University

Department: Department of Dermatology

Principal investigator: [name]

[contact]

Location: Jiangsu Province Hospital, the First Affiliated Hospital of

Nanjing Medical University

ClinicalTrials.gov ID: NCT06288607

Version: 1.0 Document date: Oct. 14, 2023

I. Background

Solar Lentigo (SL), also known as solar lentigines, or age spots, is a skin disorder associated with photoaging. It primarily appears as irregular gray or dark brown patches with a smooth surface and clear borders. Solar lentigo commonly occur in sun-exposed areas, such as the face, neck, hands, and forearms, potentially affecting appearance and causing psychological stress for patients. Current treatment options include laser, cryotherapy, chemical peeling, topical medications, and combination therapies. Among these, laser therapies, particularly Q-switched lasers, are considered the most effective single therapy, as they can precisely target treatment areas through selective photothermolysis. However, this method is influenced by skin color and carries risks of pain, redness, and hyperpigmentation.

High-Intensity Focused Ultrasound (HIFU) is a technique that focuses high-frequency ultrasound on selected tissue areas within the body. By utilizing thermal effects, cavitation effects, and mechanical effects, HIFU can create instantaneous temperatures exceeding 65°C in the focal zone, stimulating collagen regeneration and remodeling, thus achieving skin tightening. It is widely used in skin rejuvenation treatments. Both micro- and macro-focused ultrasound have been shown to be effective non-invasive treatments for skin rejuvenation. Recent studies have shown that HIFU can significantly reduce UVB-induced epidermal melanin deposition, a finding confirmed in animal models of melasma and clinical studies. This effect may be related to the vibration and friction of the pigment caused by ultrasound, mechanically disrupting and eliminating melanin and pigment fragments in the superficial epidermis and dermis. Moreover, the absorption of ultrasound energy does not rely on skin pigmentation, which can reduce adverse reactions in individuals with darker skin tones, suggesting that HIFU may serve as an alternative treatment for solar lentigo.

II. Objective

Primary Objective: This study aims to evaluate the efficacy and safety of high-intensity macro-focused ultrasound in treating facial solar lentigo, as well as its additional effects on the skin using both subjective and objective assessment methods.

III. Study Design:

This study was a prospective, single-center trial, recruited from the First Affiliated Hospital of Nanjing Medical University from November 2023 to February 2024. This trial was approved by the ethics committee (No. 2023-SR-708). All participants have signed written informed consents.

The treatment involves using two ultrasound devices with different focal depths of 3.0 mm (D3.0) and 4.5 mm (D4.5) (MFUS One, Hunan Peninsula Medical Technology Co., Ltd., China) on both sides of the face. After the procedure, an ice pack will be

applied to the treated area for 10 minutes to help reduce redness and swelling. Follow-up visits will be scheduled at 2, 4, 6, and 8 weeks after the treatment. During these visits, clinical images and non-invasive skin assessments will be conducted to monitor your progress.

IV. Study Population

Inclusion Criteria:

- 1.adults between 18 and 70 years old, regardless of gender;
- 2.those who comply the clinical diagnostic criteria for solar lentigo on both sides of the face;
- 3.patients understand and are willing to participate in this clinical trial and voluntarily sign an informed consent form;

Exclusion Criteria:

- 1. Women who are pregnant or breastfeeding, or who plan to become pregnant during the trial period;
- 2.those who are allergic to medical condensation gel;
- 3.those with photosensitive diseases, immune deficiencies, or those who are taking immunosuppressants;
- 4.those with scar physique;
- 5.those with inflammatory or infectious skin diseases;
- 6.those who have systemically used retinoic acid in the last six months or topically applied retinoic acid drugs in the last three months, or have a history of sun exposure in the four weeks prior to treatment;
- 7.those who have undergone high-intensity focused ultrasound treatment within the last six months;

V. Procedures

Before the treatment, a 2-3mm layer of medical cooling gel will be evenly applied to your face. Two macro-focused handpieces with focal depths at 3.0 mm (D3.0) and 4.5 mm (D4.5) were employed on both cheeks (MFUS One, Hunan Peninsula Medical Technology Co., Ltd., China), targeting both the lesional area and surrounding non-lesional regions while avoiding the periorbital and perioral areas. After the procedure, an ice pack will be applied to the treated area for 10 minutes to help reduce

redness and swelling. Follow-up visits will be scheduled at 2, 4, 6, and 8 weeks after the treatment. During these visits, clinical images and non-invasive skin assessments will be conducted to monitor the improvement. For non-invasive skin assessment, skin elasticity (R-value) and transepidermal water loss (TEWL) were measured using a Cutometer Dual MPA580 (Courage Khazaka Electronic GmbH, Köln, Germany) and Tewameter Hex (Courage Khazaka Electronic GmbH, Köln, Germany), respectively.

VI. Outcome Measures

1. Primary Outcome

Title: Lab* Values of Lesional Area Using Dermoscopy and ImageJ

Description: This outcome measure involves the assessment of lesional areas in dermoscopy images, with the Lab* conversion of pigmentation intensity performed using ImageJ software. L represents the lightness (brightness) of the lesion, where higher L values indicate lighter lesions (improvement). a and b represent the chromatic components (red-green and yellow-blue). Lower values in these components indicate lighter pigmentation, while higher values suggest darker lesions.

Time Frame: week0, week2, week4, week6 and week8

2. Primary Outcome

Title: Physician Global Aesthetic Improvement Scale

Description: The Physician Global Aesthetic Improvement Scale (PGAIS) is a 5-point scale used to rate the global aesthetic improvement in appearance compared to baseline, as judged by the investigator. The scale ranges from -1 (worsening) to 3 (very much improved). The higher score indicates the better improving effect.

Time Frame: week2, week4, week6 and week8

3. Primary Outcome

Title: Subjective Global Aesthetic Improvement Scale

Description: The Subjective Global Aesthetic Improvement Scale (SGAIS) is a 5-point scale used to rate the global aesthetic improvement in appearance compared to baseline, as judged by the patients. The scale ranges from -1 (worsening) to 3 (very much improved). The higher score indicates the better improving effect.

Time Frame: week2, week4, week6 and week8

4. Primary Outcome

Title: Transepidermal Water Loss (TEWL) Measurement of Lesional Area

Description: This outcome measure involves the assessment of transepidermal water loss (TEWL), which quantifies the amount of water evaporating through the skin. TEWL is a key indicator of skin barrier function and hydration levels. In this study, TEWL was measured using Tewameter Hex (Courage Khazaka Electronic GmbH) that records the rate of water loss through the skin in g/m²/h (grams per square meter per hour). Lower TEWL values (less water loss) suggest an improved skin barrier, which is typically the result of effective treatment and increased skin hydration.

Time Frame: week0, week2, week4, week6 and week8

5. Primary Outcome

Title: Skin Elasticity Measurement of Lesional Area

Description: Skin elasticity was assessed using Cutometer Dual MPA580 (Courage Khazaka Electronic GmbH, Köln, Germany), which measures the skin's resistance to deformation and recovery after deformation. The R-value represents the ratio of skin's ability to resist deformation and its ability to return to its original shape Higher R-values (greater elasticity) suggest that the skin is more resilient and can return to its original shape after deformation, indicating healthy skin with good elasticity and tone.

Time Frame: week0, week2, week4, week6 and week8

IV. Statistical Analysis:

For dermoscopy images, ImageJ software was utilized to perform Lab* conversion on both the lesional and surrounding non-lesional areas. The skin elasticity (R-value), TEWL, skin chroma (Lab* values), and Global Aesthetic Improvement Scale (GAIS) scores were analyzed using repeated-measures analysis of variance (RM-ANOVA) with Greenhouse-Geisser correction to evaluate the statistical significance of treatment effects over time. When interaction effects were observed, simple effects analysis was performed to identify the specific source of the interaction. In cases where no interaction effects were found, the main effects were analyzed. Statistical significance was set at p < 0.05 (two-tailed). All statistical analyses were conducted using SPSS Statistics for Windows (version 26.0; IBM Corp.).

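### PGAIS, one of five primary outcomes, is an investigator rating against baseline with no masking or untreated comparator described; scoring coded, order-randomised, visit-mixed photograph pairs would limit expectation bias cheaply

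*Combined protocol and SAP*

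**What the plan says.** Section VI (Outcome Measures) labels five outcomes as primary: Lab* colour values, PGAIS, the patient-rated scale (SGAIS), transepidermal water loss (TEWL) and skin elasticity. PGAIS is a 5-point score from -1 to 3, higher being better, rated "compared to baseline, as judged by the investigator". Its entry gives "Time Frame: week2, week4, week6 and week8", so there is no week-0 score. SGAIS has the same form but is rated "compared to baseline, as judged by the patients".

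Sections III and V have both handpieces used on both sides of the face, with the surrounding non-lesional skin treated as well. No untreated, sham or active control appears. On images, section V says: "During these visits, clinical images and non-invasive skin assessments will be conducted to monitor the improvement". It does not link those images to the PGAIS rating.

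The Statistical Analysis section analyses GAIS scores, along with the instrument measures, by "repeated-measures analysis of variance (RM-ANOVA) with Greenhouse-Geisser correction to evaluate the statistical significance of treatment effects over time". It adds: "When interaction effects were observed, simple effects analysis was performed to identify the specific source of the interaction". The second factor behind any interaction is not named.

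The plan therefore gives the rater's role, the reference point, the scale and the visits. It does not give masking, the number of raters, or whether rating is live or from photographs.

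**The concern.** The investigator knows that every participant was treated and, in an ordinary visit, knows which visit it is. The score is itself a judgement of improvement, so expectation can enter it directly. With no untreated side or group, nothing in the data separates that expectation from benefit.

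Two quantities could be affected, in different ways. The mean PGAIS is exposed to any upward bias. The planned test over time compares only the post-treatment visits, so it is exposed only if the bias changes from visit to visit, for example because the rater expects more improvement later. In that case the test could report an effect over time when the skin has not changed.

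**Working it through.** The documents give no sample size, SD, correlation or bias for PGAIS, so there is no planned figure to reproduce. What follows is an illustration.

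**Inputs from the plan.** Four visits (weeks 2, 4, 6, 8); scale -1 to 3; RM-ANOVA with Greenhouse-Geisser correction; two-sided 0.05.

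**Assumed inputs.** True change zero; SD 0.8; within-person correlation ρ = 0.5; n = 20, 30, 50; one-way model over visits.

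**Score model.** The underlying rating for person i at visit t is b_t + SD × (√ρ × u_i + √(1-ρ) × e_it), with u and e standard normal and b_t the rater bias. The score is this value rounded to a whole number and limited to -1 to 3.

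**1. Mean score under a constant bias b.** The expected score is -1 + Σ Φ((b - c)/SD) over the cut points c = -0.5, 0.5, 1.5, 2.5.
- b = 0: -1 + Φ(0.625) + Φ(-0.625) + Φ(-1.875) + Φ(-3.125) = 0.031. It is not zero because the scale is asymmetric.
- b = 0.5: -1 + Φ(1.25) + Φ(0) + Φ(-1.25) + Φ(-2.5) = -1 + 0.894 + 0.500 + 0.106 + 0.006 = 0.506.
- b = 0.10 and 0.25 give 0.123 and 0.265.

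Nearly all of the bias passes into the mean, as it must when there is no comparator.

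**2. Planned test over weeks 2 to 8.** A constant added at every visit cancels in the differences between visits. Growth means a linear rise from 0 at week 2 to the stated value at week 8 (0, b/3, 2b/3, b). Rejection rates from 10,000 simulated trials per setting:

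| Bias | n = 20 | n = 30 | n = 50 |
|---|---|---|---|
| None | 4% | 4% | 5% |
| Constant 0.5 | 4% | 5% | 5% |
| Growth to 0.10 | 5% | 7% | 8% |
| Growth to 0.25 | 13% | 21% | 35% |
| Growth to 0.5 | 50% | 72% | 93% |

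*Sensitivity.* Over SD 0.6-1.0 and ρ 0.3-0.7, growth to 0.10 gives 5-7% at n = 20 and 6-14% at n = 50; growth to 0.25 gives 8-27% and 19-68%. Without rounding, growth to 0.25 gives about 16-47% for n = 20 to 50. A side-by-time model with the same bias on both sides (assumed variance shares: person 0.5, person-by-time 0.2, residual 0.3) gives a time main effect of 6/8/11% for growth to 0.10 and 19/30/51% for growth to 0.25. The pattern does not depend on the one-way choice.

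**3. Effect of masked pairs.** Suppose the rater recognises which image is baseline in a fraction r of pairs. In the rest, the bias falls on either image with equal chance.
- *Mean, constant bias 0.5.* The expected score is r × 0.506 + (1 - r) × (0.506 - 0.388)/2, where -0.388 is the expected score at b = -0.5. For r = 0, 0.25, 0.5, 0.75 this is 0.059, 0.171, 0.283, 0.394. The excess of 0.059 over 0.031 at r = 0 is the residual from mapping a symmetric judgement to an asymmetric scale.
- *Time test, growth to 0.5.* If the visit is hidden, a recognised pair can carry only the visit-average bias. Rejections are then about 3-5% at any recognition rate, including r = 1.

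**The case against.** The strongest reply is that this is the known limit of an unmasked rating in a single-arm study. The objective openly combines subjective and objective measures, and three of the five primary outcomes (Lab*, TEWL, elasticity) are instrument-based. The planned test is unharmed by a constant bias, growth to 0.10 barely moves it, and nothing in the documents shows growth at all. Every size above comes from assumptions, and rounding alone moves the growth-to-0.25 figures by several points. All of this stands. It limits how serious the point is, but not the exposure of the mean PGAIS, which follows from the design without any simulation.

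The remedy also has limits. It needs a week-0 clinical photograph. Hiding the label does not hide the face from an investigator who has met the patient. Someone or something other than the rater must code the files. These are real costs, and the fix below allows for them.

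A reader might infer more than the documents support:
- *That a significant PGAIS result over time would be spurious.* That needs a growing bias, which is not shown.
- *That no rating method is given.* The scale, reference point, rater role and visits are stated; masking and the live-or-photograph question are not.
- *That no baseline photographs exist.* The sentence on clinical images concerns follow-up visits, but it is not a full list of assessment times, since Lab*, TEWL and elasticity have week-0 values.
- *That recognising the order undoes the protection of the time test.* That would require the rater still to know the visit, which the mixing is meant to hide.

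**Conclusion.** The point holds in limited form. As written, the plan lets rater expectation raise the mean PGAIS, and no feature of the design separates it from improvement. The planned RM-ANOVA keeps its error rate under a constant bias and is inflated only if the bias grows across visits. If it did, with SD 0.8, correlation 0.5 and n = 20 to 50, rejections would be about 5-8% for growth to 0.10 and about 13-35% for growth to 0.25 (about 16-47% unrounded). These figures show direction and rough scale; they are not estimates for this trial.

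The exposure through the investigator's rating is confined to PGAIS. SGAIS has the same exposure through the patient, and masked reading cannot reach it. This is a cheap, worthwhile improvement, between optional and recommended, and not a fault that undermines the trial. Masking of the ImageJ regions and the choice of RM-ANOVA model for GAIS are separate points.

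**What to change.** 1. Take, or confirm, a standardised clinical photograph at week 0, comparable with the follow-up images.
2. After the last visit, have the same investigator score PGAIS from coded baseline/follow-up pairs in random left-right order, with patient label, date and visit hidden and weeks 2, 4, 6 and 8 mixed.
3. The rater records which image looks better and by how much. Map this to the stated -1 to 3 scale by a rule fixed in advance.
4. Record the rater's guess of the order for each pair and report the recognition rate.
5. Use the masked score for the primary PGAIS analysis and keep any live rating as supportive.
6. If no comparable week-0 image exists, mask the visit only where possible and report PGAIS as an unmasked, uncontrolled rating.

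Hiding the visit protects the test over time. Hiding the order protects the mean, and that protection fades as recognition rises, so step 4 matters.

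**Cost.** At most one extra photograph per participant, plus file coding by a script or someone other than the rater. Four ratings per participant make 4 × 20 = 80 to 4 × 50 = 200 pairs, or 1.3 to 3.3 hours at an assumed one minute each. If sides are scored separately this doubles to 160-400 pairs and 2.7 to 6.7 hours. No extra visit or assessor is needed. If the visits are already complete, stored images can be re-read.

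**Downsides.** Slightly less information than a live view, possible recognition of the patient or the order, and a small upward residual from the mapping (0.059 against 0.031 in the illustration). The change does not help SGAIS or replace a control.

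### PGAIS and SGAIS are analysed only as mean scores compared between visits, so the plan neither tests improvement against no change nor shows how many patients worsened

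*Combined protocol and SAP*

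**What the plan says.** Section VI (Outcome Measures), items 2 and 3, lists the physician-rated and patient-rated Global Aesthetic Improvement Scales as primary outcomes. The physician version "is a 5-point scale used to rate the global aesthetic improvement in appearance compared to baseline, as judged by the investigator"; the patient version "is a 5-point scale used to rate the global aesthetic improvement in appearance compared to baseline, as judged by the patients". Both carry the same scoring text: "The scale ranges from -1 (worsening) to 3 (very much improved). The higher score indicates the better improving effect". Both are collected on the same schedule, "Time Frame: week2, week4, week6 and week8", so neither has a week 0 score. That is natural, because each score is already a comparison with baseline.

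The Statistical Analysis section (the second section numbered IV) treats these scores together with the continuous measurements: "Global Aesthetic Improvement Scale (GAIS) scores were analyzed using repeated-measures analysis of variance (RM-ANOVA) with Greenhouse-Geisser correction". It then describes simple effects where an interaction appears and main effects otherwise. For these two scales it gives no frequency table by grade, no definition of a responder, no ordinal method, no comparison with no change and no count of patients who worsened.

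Section II (Objective) includes safety in the primary objective. None of the five outcomes listed in section VI is an adverse-event outcome.

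**The concern.** A global improvement scale should answer two questions: how many patients got better, and how many got worse. The planned analysis answers a third one, whether the average rating differs between weeks 2, 4, 6 and 8. A rating that is high at every visit and a rating that is zero at every visit both give a flat time course.

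Any statement of benefit from these scales would therefore rest on the size of the mean, and the mean is a poor summary on this range. Improvement can add up to 3 points per patient, whereas worsening can subtract only 1, however marked it is. A favourable mean can sit beside a sizeable share of patients who look worse.

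This matters because section I (Background) motivates ultrasound partly by the harms of laser treatment, which "carries risks of pain, redness, and hyperpigmentation". Among the listed outcomes, the -1 grade is the only place where a physician or patient records, patient by patient, a judgement that appearance has worsened. The plan never shows that count.

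**Working it through.** The plan states no figure for these scales (no sample size, standard deviation, expected score or responder threshold), so there is none to reproduce. The check is arithmetic on the scale itself.

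**Inputs**
- Five points from -1 to 3, higher being better (section VI, items 2 and 3).
- Visits at weeks 2, 4, 6 and 8, with no week 0 (same items).
- Repeated-measures ANOVA (Statistical Analysis section).
- Inferred: the points are the integers -1, 0, 1, 2, 3, and 0 means no change. Only the two end labels are printed, but a five-point range from -1 to 3 leaves little room for another reading.

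**Step 1: balance of the scale.** There is one negative grade, one zero and three positive grades. The midpoint is (-1 + 0 + 1 + 2 + 3)/5 = +1.

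**Step 2: offsetting.** One patient at +3 and three at -1 sum to 3 - 3 = 0. Three of these four patients are worse, yet the mean equals that of four unchanged patients.

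**Step 3: share worsened at which the mean reaches 0.** Let a share p score -1 and the rest score g. The mean is g(1 - p) - p, which is 0 when p = g/(g + 1).

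| Score of the improved patients (g) | Share worsened at mean 0 | Mean if half improve and half worsen, (g - 1)/2 |
|---|---|---|
| +1 | 1/2 = 50% | 0.00 |
| +2 | 2/3 = 67% | +0.50 |
| +3 | 3/4 = 75% | +1.00 |

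The first row sets the limit of the point: when improvements are only one grade, equal shares better and worse average 0 and nothing is tilted. The tilt needs improvements of two or three grades.

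**Step 4: what the time test sees.** With n patients, the time effect is built from n × Σ(visit mean - overall mean)². Adding the same constant to every visit mean leaves each difference unchanged. Visit means of +2, +2, +2, +2 and of 0, 0, 0, 0 both give a time effect of zero. The time test therefore carries no information on whether patients improved from baseline. A significant result would say only that ratings differ between follow-up visits.

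**The case against.** The strongest reply is that the planned test does not use the level of the mean, so a scale that tilts the mean cannot bias it. That stands. A reader might infer from the lopsided range that the planned test gives false positives, because symmetric rating noise is cut off only on the negative side. The documents do not support this. A simulation used normally distributed noise with no true change, rounded and capped to the scale, over four visits. It assumed a within-patient correlation of 0.6 and a constant SD of 1.5 grades. The mean was about +0.2 at every visit, but the time test rejected in 4.1% of 3,000 runs at an assumed n = 20 and 4.9% at n = 40, close to the nominal 5%. Inflation (12.3% and 25.7%) appeared only when the SD was made to grow from 0.75 to 2.0 across visits, for which the plan gives no basis.

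The noise-related shift in the mean also rests wholly on assumed SDs: +0.00 at 0.5, +0.07 at 1.0, +0.21 at 1.5 and +0.33 at 2.0. At the two larger values the model would have about 37% and 40% of unchanged patients rated as worse (P(Z < -0.5/SD)), which is extreme. It is not a ground for the point.

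Three further replies deserve weight.
- Lesional Lab* is also primary, has a week 0 value, and its L component is not capped for darkening. Darkening is therefore not invisible to the plan. Lab* is, however, also analysed through means, without a patient-level count of worsening, and it does not record how appearance was judged.
- The plan names a test and does not forbid a table of grades. True, but it does not commit to one either.
- Reporting the share at -1 cannot separate slight from severe worsening. That stands, and no reanalysis can undo it.

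A reader might also infer that the instrument should be rebuilt as a balanced -3 to +3 scale. The number of worsening grades is a matter of instrument preference, and nothing in the documents makes the present scale an error.

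**Conclusion.** The point holds as a gap in analysis and reporting for two primary outcomes. As planned, PGAIS and SGAIS yield a comparison of means between follow-up visits. This neither tests improvement against no change nor shows who worsened. The possible masking has a definite size on the plan's own range: one +3 cancels three -1 scores, and a positive mean is compatible with up to 75% of patients worsened if all the rest score +3, or up to 67% if they score +2. These are limits of what the mean can conceal; the documents give no data on how patients will be distributed. The only assumptions are integer grades and 0 as no change.

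The verdict does not extend to three stronger readings: that mixed outcomes always average to apparent benefit (equal shares at +1 and -1 average 0), that the planned test has an inflated error rate, or that the scale itself must be changed.

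**What to change.** In the Statistical Analysis section, for PGAIS and SGAIS only, replace the mean-based repeated-measures ANOVA with:

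1. The number and percentage of patients in each grade (-1, 0, 1, 2, 3) at weeks 2, 4, 6 and 8, with the meaning of grades 0, 1 and 2 printed.
2. At week 8, the proportion improved (score 1 or more) and the proportion worsened (score -1), each with an exact 95% confidence interval.
3. A comparison of visits by an ordinal method, such as the Friedman test or a cumulative-logit model that allows for repeated ratings of the same patient.
4. A requirement that the worsened proportion stand beside any claim of improvement.

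The cost is a few lines of SAP wording and one table per scale from scores the plan already collects; no form or visit changes. If scores have already been analysed, the revised analysis should be labelled as added afterwards.

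There are two downsides. Proportions are slightly less precise than a mean. The plan gives no sample size, but as a guide, if no patient worsened the exact upper limit would be 1 - 0.025^(1/n): 16.8% at an assumed n = 20 and 8.8% at n = 40. And how severe the worsening was within grade -1 remains unknown.

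### PGAIS and SGAIS are change scores with no week-0 value, so no effect named in the planned RM-ANOVA tests whether patients improved

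*Combined protocol and SAP*

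**What the plan says.** In VI. Outcome Measures, PGAIS (outcome 2) and SGAIS (outcome 3) are both labelled primary. PGAIS is used to "rate the global aesthetic improvement in appearance compared to baseline, as judged by the investigator"; SGAIS is used to "rate the global aesthetic improvement in appearance compared to baseline, as judged by the patients". Both carry the line "Time Frame: week2, week4, week6 and week8". For both, only the end points are labelled: "The scale ranges from -1 (worsening) to 3 (very much improved"). The meaning of 0, 1 and 2 is not given.

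The other three primary outcomes (Lab*, TEWL, elasticity) carry the line "Time Frame: week0, week2, week4, week6 and week8".

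IV. Statistical Analysis (the second section with that number) puts all five outcomes through one method: "Global Aesthetic Improvement Scale (GAIS) scores were analyzed using repeated-measures analysis of variance (RM-ANOVA) with Greenhouse-Geisser correction". The stated aim is to judge how treatment effects behave over time. The section names three kinds of effect: interactions, simple effects when an interaction is seen, and otherwise main effects: "In cases where no interaction effects were found, the main effects were analyzed". An interaction needs a second factor, and the plan does not name one. For these two scales there is no test against a no-change value, no responder proportion, no confidence interval, and no rule that enters week 0 as 0.

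**The concern.** When week 0 is among the repeated measurements, the time effect includes a comparison with baseline. That is the case for Lab*, TEWL and elasticity. PGAIS and SGAIS are already changes from baseline, so evidence of improvement lies in how far the scores are from no change. The time effect looks only at how far the four follow-up visits are from each other.

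The p-value can therefore mislead in both directions. A benefit that is present at week 2 and stays the same to week 8 is expected to give a non-significant time effect. Scores that move between visits are expected to give a significant one, whether the benefit is growing, fading, or an early worsening that resolves. Efficacy by subjective as well as objective assessment is part of the primary objective, and these are the only two rating-based primary outcomes.

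**Working it through.** The plan states no sample size, power, SD or effect size, so there is no figure of its own to reproduce. Step 1 needs no assumptions; steps 2 to 4 are illustrations with assumed inputs.

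**1. Algebra.** Let Y_ij be the score of patient i (i = 1…n) at visit j, with k = 4 visits (weeks 2, 4, 6, 8).

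- SS_time = n Σ_j (Ȳ_.j − Ȳ_..)²
- SS_error = Σ_i Σ_j (Y_ij − Ȳ_i. − Ȳ_.j + Ȳ_..)²
- F = [SS_time/(k − 1)] / [SS_error/((k − 1)(n − 1))], on 3ε and 3(n − 1)ε degrees of freedom
- ε = tr(C)² / [(k − 1) tr(C²)], where C is the double-centred covariance matrix of the visits

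Replace every Y_ij by Y_ij + c. Each mean rises by c, so c cancels in both sums of squares, and covariances do not change. F, ε and p are therefore unchanged. As a numerical check on one simulated data set of 20 patients, p = 0.489 for the scores as they stood, for the scores minus 1, and for the scores minus 5.

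For a 2 × 4 layout (any two-level factor by four visits), the time, factor and interaction contrasts applied to a constant mean all give exactly 0. Simple effects are differences within one level of the other factor, so the same holds for them.

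The sum of squared deviations of the visit means, which drives F, shows what is lost:

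- Means 1.5, 1.5, 1.5, 1.5: sum 0, the same as for means 0, 0, 0, 0.
- Means 0.5, 1, 1.5, 2 (average 1.25): 0.75² + 0.25² + 0.25² + 0.75² = 1.25. The reverse order 2, 1.5, 1, 0.5 also gives 1.25.

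The level and the direction of the scores both drop out.

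**2. Simulation A.** Assumed: 0 = no change, between- and within-patient SD 0.6, scores rounded and limited to −1 to 3, n = 15/20/30/60, 5000 runs, two-sided 0.05. Entries are the percentage of trials significant; visit means are those before rounding.

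| True mean at weeks 2, 4, 6, 8 | Time effect (GG-corrected) | Week-8 exact sign test against 0 |
|---|---|---|
| 0 throughout | 4.0 / 4.3 / 4.1 / 4.6 | 2.1 / 2.3 / 3.1 / 2.8 |
| +0.5 throughout | 3.4 / 4.0 / 4.1 / 4.8 | 35.2 / 49.1 / 73.2 / 97.4 |
| +1.5 throughout | 4.0 / 3.9 / 4.4 / 4.9 | 99.98 / 100 / 100 / 100 |
| 1.0, 0.7, 0.3, 0 | 94.3 / 98.9 / 99.9 / 100 | 2.3 / 2.5 / 3.1 / 3.2 |
| 0, 0.5, 1.0, 1.5 | 100 at every n | not run |

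With +0.5 throughout, a Wilcoxon signed-rank test on each patient's four-visit mean (1000 runs) is significant in 79.8 / 88.4 / 98.1 / 100%.

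With a second within-patient factor of two levels and +1.5 in every cell (n = 15/30/60): time 4.1 / 4.5 / 4.9%, factor 4.9 / 4.8 / 4.8%, interaction 3.4 / 4.7 / 5.1%.

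**3. Sensitivity to the SDs.** Both SDs varied over 0.3, 0.6 and 1.0 (n = 15 and 60, 3000 runs). With +1.5 throughout, the time effect is significant in 3.5–5.0% and the sign test in 86–100%. With the fading profile, the time effect is significant in 51–100%.

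**4. Simulation B, other assumptions.** SD 0.8, correlation between visits 0.6, n = 10/20/30, 3000 runs; the comparator is a one-sample t test of the patient mean against 0, counted only when it points to improvement.

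- +1 throughout: time effect 3.2 / 4.5 / 4.3%; test against 0, 98.9 / 100 / 100%.
- −0.8, −0.5, −0.2, 0 (worse, then back to no change): time effect 53 / 92 / 99%; test against 0, 0% at every n.
- Rising 0.5 to 2, and fading 2 to 0.5: time effect at least 99.7% in both.

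**The case against.** The strongest reply is that the planned test is valid for a different question. Comparing visits is a proper way to study the time course of a change score, and the mean scores would show improvement descriptively. If the mean were 0 at every visit, the time effect would be null, so a significant result is evidence against no change throughout. A benefit that builds from week 2 to week 8 would be detected in the right direction. The model also contains a grand-mean term that could be tested against 0.

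Most of this is true, and it limits the point without removing it. A significant time effect shows neither level nor direction, and it has no power against a constant benefit. Whether it helps depends on a time profile that is not known in advance. The plan does not name or use the grand-mean term, and a test against 0 needs a defined zero.

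Two further objections stand in part. In the fading example there is real improvement at week 2, so the significant result is not a false signal of change; what it cannot show is whether benefit remains, and a week-8 test asks exactly that. The simulated rates also rest on assumed inputs, and the figures near 5% only restate the significance level when the visit means are equal. The evidence is the algebra; the simulations show what it means in practice.

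It is also fair that the other three primary outcomes have a baseline comparison, so efficacy is not left untested overall. That does not supply a test of improvement for these two.

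**Conclusion.** The concern holds, and the plan is wrong as written for two of its five primary outcomes. That every named effect is unchanged when a constant is added to all scores is exact; it does not depend on the sample size, the variance, the meaning of 0, or the identity of the second factor. Following the plan gives a null result for a stable benefit (about 3–5% significant in every constant-mean setting examined) where a test against 0 would usually detect it. The power figures for tests against 0 depend on the assumed sample sizes and SDs and on 0 meaning no change, which is plausible from the end labels but not stated. Lab*, TEWL and elasticity are not affected in this way.

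**What to change.** In IV. Statistical Analysis, with the scale labels added in VI. Outcome Measures:

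1. Label all five scale points, and state that 0 means no change if that is the scale used.
2. For each of PGAIS and SGAIS, name one efficacy test against 0 and what it is applied to. Either an exact sign test or a Wilcoxon signed-rank test will do, at one named visit (for example week 8, the last visit) or on each patient's mean over the four visits. The first asks whether benefit is present at that visit, the second whether there is benefit on average; the plan should choose one.
3. Report the proportion of patients scoring at least 1, with an exact 95% CI.
4. Keep the RM-ANOVA over weeks 2 to 8 as a description of the time course only, and name the second factor if there is one.
5. State that a test against 0 shows change from baseline and not a causal effect, because no untreated control is described.

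The cost is a few sentences, with the same data and software. The section is written in the past tense; if the scores have already been analysed, the added test must be labelled post hoc.
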